### 8.4.3 Physical examination

#### 8.4.3.1 Complete physical examination

A complete physical examination will be performed throughout the study, according to the tabular schedules of procedures.

The complete physical examination will include cardiac and respiratory function via auscultation, temperature measurement, and review of all body systems.

Clinically significant physical examination findings will be reported as AEs.

### **8.4.3.2 Brief physical examination**

A brief physical examination will be performed throughout the study, according to the tabular schedules of procedures.

The brief physical examination will include a review of the following body systems:

- Cardiovascular
- Pulmonary
- Abdominal (hepato-gastrointestinal)
- Dermatologic

Clinically significant physical examination findings will be reported as AEs.

## **8.4.4 Neurological examination**

### **8.4.4.1 Complete neurological examination**

A complete neurological examination will be performed throughout the study, according to the tabular schedules of procedures.

The complete neurological examination will include selected assessment of: general neurological status (level of consciousness, mental status, speech), cranial nerves, reflexes, motor system (general motor status, muscle strength, muscle tone), coordination/cerebellar function, and sensation.

Clinically significant neurological findings will be reported as AEs. Summaries of shift from Baseline to Last Visit will be provided based on categories normal, abnormal, not clinically significant, and abnormal, clinically significant. A listing of neurological examination findings from the complete neurological examination will also be provided.

### **8.4.4.2 Brief neurological examination**

A brief neurological examination will be performed throughout the study, according to the tabular schedules of procedures.

The brief neurological examination will include selected assessment of: general neurological status, reflexes, muscle strength, and coordination/cerebella function.

Clinically significant neurological findings will be reported as AEs.

A listing of neurological examination findings from the brief neurological examination will also be provided. No summaries of these results are planned.

## **8.4.5 Vagus nerve stimulation**

VNS status is recorded throughout the study, according to the tabular schedules of procedures, only for those subjects with an implanted VNS device.

A listing of VNS status will be provided only for those subjects with an implanted VNS device.

#### 8.4.6 Tanner stage assessment

Tanner stage will be assessed throughout the study, according to the tabular schedules of procedures.

The investigator or qualified designee will evaluate the subject's sexual development using the 3-item Tanner scale (ie, for females: breasts, pubic hair, and overall stage; and for males:

genitals, pubic hair, and overall stage). The investigator should use clinical judgment in deciding which subjects are selected for evaluation of Tanner Stage (ie, those subjects who are pubescent at Visit 1 [entry to study] or who will enter puberty during the course of the study).

A shift table will be produced showing the change in overall Tanner stage (1-5) from Baseline to Last Visit, by gender.

#### 8.4.7 Assessment of suicidality

Suicidality will be assessed by trained study personnel using the C-SSRS (Columbia University Medical Center, 2008). This will be completed according to the tabular schedules of study procedures.

For subjects  $\geq 6$  years of age, this scale will be used for screening as well as to assess suicidal ideation and behavior that may occur during the study. All subjects who are  $\geq 6$  years of age will complete the Baseline/Screening version of the C-SSRS at entry to the study and will complete the Since Last Visit version at subsequent visits. If a subject becomes 6 years of age during the study, the Already Enrolled version of the C-SSRS should be used at the first visit at which the subject is 6 years of age and use the Since Last Visit version at subsequent visits.

For subjects  $< 6$  years of age, the C-SSRS is not validated and will not be used. For those subjects, signs and symptoms of depression will be assessed at each visit.

Subject data listings of the data for the C-SSRS will be provided. No summaries of these results are planned.

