10 ASSESSMENT OF SAFETY

10.1 Adverse events

10.1.1 Definition of adverse event

An adverse event (AE) is any untoward medical occurrence in a patient or clinical investigation subject administered a pharmaceutical product that does not necessarily have a causal relationship with this treatment. An AE can therefore be any unfavorable and unintended sign (including an abnormal laboratory finding), symptom, or disease temporally associated with the use of a medicinal (investigational) product, whether or not related to the medicinal (investigational) product.

In order to ensure complete safety data collection, all AEs occurring during the study (ie, after the signing of the ICF), including any pretreatment and posttreatment periods required by the protocol, must be reported in the eCRF even if no investigational product was taken but specific study procedures were conducted. This includes all AEs not present prior to the initial visit and all AEs that recurred or worsened after the initial visit. For results disclosure, only TEAEs are applicable.

Signs or symptoms of the condition/disease for which the investigational product is being studied should be recorded as AEs only if their nature changes considerably or their frequency or intensity increases in a clinically significant manner as compared to the clinical profile known to the investigator from the subject's history or the Baseline Period.

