10.1.3 Description of adverse events

When recording an AE, the investigator should use the overall diagnosis or syndrome using standard medical terminology, rather than recording individual symptoms or signs. The eCRF and source documents should be consistent. Any discrepancies between the subject's own words

on his/her own records (eg, diary card) and the corresponding medical terminology should be clarified in the source documentation.

Details for completion of the Adverse Event eCRF (including judgment of relationship to study drug) are described in the eCRF Completion Guidelines.

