10.1.7 Overdose of IMP

Excessive dosing (beyond that prescribed in the protocol and including overdose) should be recorded in the Drug Accountability or Study Drug Dosing module of the eCRF. Any SAE or nonserious AE associated with excessive dosing must be followed as any other SAE or nonserious AE. These events are only considered AEs or SAEs if there are associated clinical signs and symptoms or if the act of taking the excess medicine itself is an AE or SAE (eg, suicide attempt).

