10.6.1 Liver function tests and evaluation of PDILI

The PDILI IMP discontinuation criteria for this study are provided in Section 10.6.1.2, with the accompanying required follow-up investigation and monitoring detailed below. All PDILI events must be reported as an AE and reported to the study site and sponsor within 24 hours of learning of their occurrence. Any PDILI event that meets the criterion for potential Hy’s Law must be reported as an AE of special interest (see Section 10.3), and, if applicable, also reported as an SAE (see Section 10.2).

Evaluation of PDILI consists of the diagnostic testing and continued monitoring included in Table 10–3 (specific tests dependent on laboratory results and corresponding symptoms) and consultation with a local hepatologist (if applicable; discussed in Section 10.6.1.1). The local

hepatologist is the expert usually consulted by the treating physician for assessment and management of potential hepatic disease. This would usually be a hepatologist, but may be a gastroenterologist. Additional investigation and monitoring may be required and adapted based on the diagnosis after the cause of the liver injury/abnormality is confirmed (details in Section 10.6.1.4).

The results of all monitoring, including laboratory testing and other testing, should be made available to the study site and sponsor.

All initial tests resulting in abnormal hepatic laboratory values need to be repeated, but appropriate medical action must not be delayed waiting for the repeat result.

If tests are done locally for more rapid results, a concurrent sample should also be sent to the central laboratory whenever possible. Medical care decisions are to be made initially using the most rapidly available results and a conservative approach must be taken if the results from the 2 laboratory tests are significantly different. Data from the local and central laboratory are to be recorded on the applicable eCRF pages.

When IMP is discontinued, all concomitant medications and herbal supplements that are not medically necessary should also be discontinued. In these cases, the investigator should also consider dose reduction for medically necessary concomitant medication and consider changing any medically required concomitant medication known to be hepatotoxic to a suitable alternative.

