10.8 Other safety measurements

10.8.1 Physical examination

Physical examinations will be performed according to the tabular schedules of study procedures (Section 5.2) by a medically qualified clinician licensed to perform the examination. Clinically significant physical examination findings are to be reported as AEs.

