10.8.6 Assessment of suicidality

Suicidality will be assessed by trained study personnel using the C-SSRS (Columbia University Medical Center, 2008). This scale will be used for subject's eligibility for the study as well as to assess suicidal ideation and behavior that may occur during the study.

The C-SSRS will be completed according to the tabular schedules of study procedures (Section 5.2). This scale will be completed for subjects ≥ 6 years of age. The "Since Last Visit" version of the C-SSRS should be used. If a subject becomes 6 years of age during the study, the

“Already Enrolled” version of the C-SSRS should be used at the first visit at which the subject is 6 years of age and the “Since Last Visit” version at subsequent visits.

The C-SSRS is not validated for subjects <6 years of age and will not be used for this population. Subjects should be monitored for any changes in mood, ideas, or behavior for warning signs of depression. The investigator should be aware of common warning signs that might be a signal for risk of depression. For common signs and symptoms of depression in children younger than 6 years old, reference should be made to the current version of the Diagnostic and Statistical Manual of Mental Disorders. Parents and caregivers should also be advised accordingly and effort should be made at clinic visits to specifically assess potential depression.

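### C-SSRS results are listed but never summarized, so suicidality is identifiable in planned tables only when recorded as an adverse event, and no table gives the number of subjects assessed

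*SAP*

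**What the plan says.** Protocol 10.8.6 uses the C-SSRS in subjects aged 6 or over for eligibility and also to "assess suicidal ideation and behavior that may occur during the study". On output, SAP 8.4.7 says: "Subject data listings of the data for the C-SSRS will be provided. No summaries of these results are planned".

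Two other parts of the plan touch suicidality:

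- **Withdrawal.** Under Protocol 6.3, mandatory criterion 5, a Yes to Question 4 or 5 leads to mental health referral and withdrawal. The criterion does not mention recording an adverse event (AE).
- **Adverse events.** SAP Table 12-3 lists suicidality preferred terms. SAP 8.2 tabulates them as other significant TEAEs overall, by weight band, by enrollment group and by 3-month interval.

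On what becomes an AE, Protocol 10.1.1 is broad: "any untoward medical occurrence in a patient or clinical investigation subject" given a pharmaceutical product, whether or not related to it. Protocol 10.1.7 names a suicide attempt as an example when excess dosing is itself an AE. Protocol 10.1.3 adds: "Details for completion of the Adverse Event eCRF (including judgment of relationship to study drug) are described in the eCRF Completion Guidelines".

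For other assessments there is a specific rule. Protocol 10.6.1: "All PDILI events must be reported as an AE". Protocol 10.8.1: "Clinically significant physical examination findings are to be reported as AEs". SAP 8.4.4.1: "Clinically significant neurological findings will be reported as AEs". Neither document has such a rule for the C-SSRS.

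**The concern.** Long-term safety and tolerability is the primary objective. The trial gives a dedicated suicidality scale at every clinic visit, yet what the tables identify as suicidality depends on whether an investigator judged a response to be an AE. A reader who wants the number of subjects with a positive response, and the number asked, would have to count both by hand from listings.

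The SAP does not rely on AE terms alone for its other focused safety topics. Liver safety has an AE term list and also a count of subjects meeting the PDILI criteria, with percentages based on subjects measured (SAP 8.3). Cardiac safety has AE terms and also ECG abnormality tables, with percentages of subjects assessed for the overall finding categories (SAP 8.4.2). Suicidality has an AE term list and an instrument, but no table from the instrument.

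**Working it through.** The plan states no figure to reproduce. The check is to follow each kind of C-SSRS finding to the tables it can reach.

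| Finding on the C-SSRS | Recorded as an AE | Not recorded as an AE |
|---|---|---|
| Yes to Question 4 or 5 | TEAE tables, Table 12-3 terms, discontinuations due to AEs | Disposition by primary reason (SAP 5.1). If the site does not withdraw the subject, the withdrawal-criteria category of important deviations (SAP 3.4, 5.2). Neither is specified to show suicidality |
| Ideation short of Question 4 or 5 | TEAE tables, Table 12-3 terms | Not named in criterion 5; listing only |
| Suicidal behavior | TEAE tables, Table 12-3 terms | Not named in criterion 5; listing only |

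In the last two rows the investigator could still withdraw the subject on another ground, such as best interest (Protocol 6.3, criterion 7). That would give a disposition count, again without a suicidality label.

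**Terms.** The suicidality block of Table 12-3 has 11 preferred terms, including ideation, behaviour and attempt.

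**Number assessed.** Safety tables use the Safety Set (SAP 8). The default age groups split at 4 years (SAP 3.1), and the demographic categories split at 24 months and 12 years (SAP 6.1). The CBCL/6-18 groups start at 6, but that form is used only where a validated translation exists (SAP 8.4.8), so its n is not the C-SSRS n. Subjects who turn 6 on study join the assessed group later, so a count by entry age would not give it either. A zero in the suicidality TEAE rows therefore cannot be read as zero out of a known number assessed.

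**Scheduled assessments, for a completer aged 6 or over at entry.**

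- Protocol Table 5-1, Visits 1 to 6: 6
- Protocol Table 5-2, Visits 7 to 13: 7
- Total: 6 + 7 = 13; after entry: 13 − 1 = 12
- With the Taper Visit and Safety Follow-Up Visit (Table 5-3): 13 + 2 = 15; after entry: 12 + 2 = 14

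An Unscheduled Visit for a safety or efficacy reason adds one. These counts show how much C-SSRS data is collected without a planned summary. They do not measure the size of any error.

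**The case against.** The case for leaving the SAP alone has real substance.

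- **The serious cases are not invisible.** A reader might infer that C-SSRS findings reach no table at all without an AE. The documents do not support that for Question 4 or 5, because mandatory withdrawal leads to a disposition count, or to a deviation count if the criterion is ignored. This stands and limits the point. What those tables lack is a suicidality label.
- **AE recording will probably catch clear events.** The definition is broad, and the other-significant-TEAE table is repeated with site and subject numbers, so it can be compared with the C-SSRS listing. The eCRF Completion Guidelines may give a C-SSRS rule, but they are not part of these documents. This makes a missed finding less likely without ruling it out.
- **The comparators also rest on judgment.** The physical and neurological rules apply only to clinically significant findings. That is fair. They show that a link to AE recording was written for those assessments, not that judgment was removed.
- **Listing-only output is used elsewhere,** for urinalysis, pregnancy tests, VNS status and drug accountability. The C-SSRS is not a named safety variable (Protocol 4.1, SAP 2.2) and Protocol 12.3 promises no table for it. So a reading that the SAP departs from the protocol fails.
- **Positives may be few.** Exclusion criterion 3 removes subjects aged 6 or over with any past suicide attempt, or with a Yes to Question 4 or 5 for the past 6 months. That is plausible, but a small count is informative only beside the number assessed.

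**Conclusion.** The point holds as a reporting gap. Suicidality is identifiable in the planned tables only through coded AEs. Ideation short of Question 4 or 5, or suicidal behavior, that is noted on the scale but not recorded as an AE can be absent from every planned table. The number of subjects aged 6 or over who were assessed appears nowhere. The data are not lost, since full listings are planned, and no planned estimate is shown to be wrong.

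The size cannot be estimated: the documents give neither a rate of positive responses nor the share of subjects aged 6 or over. The conclusion assumes that the eCRF Completion Guidelines do not require every positive C-SSRS response to be recorded as an AE. If they do, the risk of a missed finding largely disappears, but the missing number assessed remains.

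**What to change.** In SAP 8.4.7, replace the sentence ruling out summaries with one descriptive table:

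- **Rows:** number and percentage of subjects with any post-entry suicidal ideation, with a Yes to Question 4 or 5 shown separately; and with any post-entry suicidal behavior.
- **Data:** all scheduled and unscheduled C-SSRS assessments after Visit 1 through the Safety Follow-Up Visit.
- **Denominator:** subjects with at least one post-entry C-SSRS at age 6 or over, with that number displayed.
- **Exclusion:** responses about the time before EP0034 entry. This needs attention for subjects who turn 6 on study and first complete the Already Enrolled version.

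The cost is one extra table from data already collected, with no hypothesis test and no protocol amendment. The table does not change how AEs are recorded or counted. It shows the scale results whether or not an AE was recorded.

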#### 8.4.8 Achenbach Child Behavior Checklist

The Achenbach CBCL will be completed according to the tabular schedule of study procedures, only in countries where a validated translated version is available.

The Achenbach CBCL form is a questionnaire intended to evaluate a child's competencies and behavioral/emotional problems. Depending on the subject's age, 1 of 2 versions of the Achenbach CBCL is used. The CBCL/1½-5 is intended for use in children 18 months to 5 years and 11 months of age. For study subjects  $\geq 6$  years to  $\leq 18$  years, the CBCL/6-18 will be used.

The CBCL/1½-5 comprises 100 questions and the CBCL/6-18 comprises 120 questions. In both questionnaires, the occurrence of certain problems and behaviors (in the past 2 months for the CBCL/1½-5 version and in the past 6 months for the CBCL/6-18 version) will be scored on the following scale:

- 0=not true (as far as known)
- 1=somewhat or sometimes true
- 2=very true or often true

The CBCL/1½-5 items will be grouped according to syndrome scales in Table 8–3 and the CBCL/6-18 items will be grouped according to empirically based syndrome scales in Table 8–4. For each syndrome, a raw score will be calculated as the sum of the considered item scores.

**Table 8–3: CBCL/1½-5**

Syndrome scale	Items
Aggressive behavior	8, 15, 16, 18, 20, 27, 29, 35, 40, 42, 44, 53, 58, 66, 69, 81, 85, 88, 96
Anxious/depressed	10, 33, 37, 43, 47, 68, 87, 90
Attention problems	5, 6, 56, 59, 95
Emotionally reactive	21, 46, 51, 79, 82, 83, 92, 97, 99
Sleep problems	22, 38, 48, 64, 74, 84, 94
Somatic complaints	1, 7, 12, 19, 24, 39, 45, 52, 78, 86, 93
Withdrawn	2, 4, 23, 62, 67, 70, 71, 98
Other problems	3, 9, 11, 13, 14, 17, 25, 26, 28, 30, 31, 32, 34, 36, 41, 49, 50, 54, 55, 57, 60, 61, 63, 65, 72, 73, 75, 76, 77, 80, 89, 91, 100

**Table 8–4: CBCL/6-18**

Syndrome scale	Items
Aggressive behavior	3, 16, 19, 20, 21, 22, 23, 37, 57, 68, 86, 87, 88, 89, 94, 95, 97, 104
Anxious/depressed	14, 29, 30, 31, 32, 33, 35, 45, 50, 52, 71, 91, 112
Attention problems	1, 4, 8, 10, 13, 17, 41, 61, 78, 80
Rule-breaking behavior	2, 26, 28, 39, 43, 63, 67, 72, 73, 81, 82, 90, 96, 99, 101, 105, 106
Social problems	11, 12, 25, 27, 34, 36, 38, 48, 62, 64, 79
Somatic complaints	47, 49, 51, 54, 56a, 56b, 56c, 56d, 56e, 56f, 56g
Thought problems	9, 18, 40, 46, 58, 59, 60, 66, 70, 76, 83, 84, 85, 92, 100
Withdrawn/depressed	5, 42, 65, 69, 75, 102, 103, 111

Standardized T-scores are determined for each subject’s raw syndrome and overall scores based on the subject’s age and sex. Tables mapping each raw score to the appropriate T-score are provided in the CBCL Professional Manual. Standardized T-scores determined from each subject’s raw syndrome scale scores will be reproduced programmatically using the appropriate scoring spreadsheets.

Raw scores and change from Baseline for each CBCL/1½-5 syndrome (aggressive behavior, anxious/depressed, attention problems, emotionally reactive, other problems, sleep problems, somatic complaints, and withdrawn) will be summarized for each visit, and Last Visit.

Raw scores and change from Baseline for each CBCL/6-18 syndrome (aggressive behavior, anxious/depressed, attention problems, rule-breaking behavior, social problems, somatic complaints, thought problems, and withdrawn/depressed) will be summarized for each visit, and Last Visit.

The Calculated T-scores, raw scores, and change from Baseline in raw scores will be listed.

A decrease from Baseline (change from Baseline <0) in the CBCL syndrome raw score will indicate improvement in behavior, while an increase (change from Baseline > 0) indicates worsening.

In addition, for both the CBCL/1½-5 syndrome and /6-18 syndrome, subjects will be categorized according to the Calculated T-score as follows:

- T-score is < 65 = “Normal”
- T-score is ≥ 65 = “Borderline or Clinical range (BCR)”

Summaries of shifts from Baseline to each post-Baseline visit, and from Baseline to Last Visit will also be provided based on the CBCL calculated T-score categories of Normal and BCR. The descriptive summaries of change from Baseline and shift summaries will be presented only when a corresponding Baseline value from the same questionnaire is available.

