10.8.7 Achenbach CBCL

The Achenbach CBCL is a widely used validated questionnaire to evaluate a child’s competencies and behavioral/emotional problems. Behavioral problems will be scored by the parent(s)/legal representative(s).

Depending on the subject’s age, 2 versions of the Achenbach CBCL will be used. The CBCL/1½-5 checklist is intended for use in children 18 months to 5 years and 11 months of age (Achenbach and Rescorla, 2000). For subjects ≥6 years to <17 years of age, the CBCL/6-18 version will be used (Achenbach and Rescorla, 2001). The version of the Achenbach CBCL appropriate to each subject’s age should be administered with the following exception: For subjects who completed the CBCL/1½-5 at the Baseline assessment of the previous study and turn 6 years of age within 1 year after the Baseline assessment of the primary study, the CBCL/1½-5 should be completed for 1 year after the Baseline assessment of the primary study, and subsequently the CBCL/6-18 should be completed. The Achenbach CBCL will only be administered in countries where a validated translated version is available.

The Achenbach CBCL will be completed according to the tabular schedules of study procedures (Section 5.2). The completion of the Achenbach CBCL will require approximately 45 minutes.

In both questionnaires, the occurrence of certain problems and behaviors in the past 6 months will be scored on the following scale:

- 0=not true (as far as known)
- 1=somewhat or sometimes true
- 2=very true or often true

Eight syndrome scores will be calculated from these questions, which will in turn be summarized by 2 composite scores. Additionally, for each score on the question, syndrome, and total level, categorizations based on a normative sample will be used to evaluate normal, borderline, or clinically relevant behavior.

In addition, the CBCL/6-18 includes ratings related to performance in school, activities in leisure time, and special interests.

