12.3 Planned safety analyses

The long-term safety of LCM at individualized doses will be evaluated by means of the safety analyses. Summary tables will be presented over the Treatment Period by 3-month periods and by categories of total duration of exposure. All safety variables will be analyzed by descriptive methods on the SS. Treatment-emergent AEs will be defined as those events which started on or after the date of first EP0034 dose of LCM, or whose severity worsened on or after the date of first EP0034 dose of LCM. Adverse events which occur within 30 days after last dose of LCM will be considered treatment emergent. Treatment-emergent AEs will be summarized by categories of total duration of exposure, 3-month period, Medical Dictionary for Regulatory Activities (MedDRA[®]) Primary System Organ Class and Preferred Term in incidence tables. Separate tables will be provided by categories of total duration of exposure for AEs leading to withdrawal from the study and SAEs.

The safety variables such as changes in ECG, vital signs, laboratory parameters, height, body weight measurements, and Tanner Stage scores will be analyzed descriptively. The results for occurrence of these variables during long-term treatment will be summarized overall, and by visit. Subjects will be grouped by dose for summary purposes. The procedure for grouping

subjects by dose will be defined in the SAP. In addition, shift tables may be used to evaluate the number and percentage of subjects having a different post-Baseline status when compared to their Baseline status.

Changes from Baseline in laboratory, ECG, and vital sign values will be tabulated. In addition, physical and neurological examination abnormalities will be listed by visit. Markedly abnormal values will be summarized descriptively for laboratory, vital sign, body weight, and ECG parameters.

Achenbach CBCL scores, BRIEF/BRIEF-P scores, and Bayley-III scores and the respective change from primary LCM study Baseline scores will be analyzed in a descriptive manner.

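### The CBCL shift tables cannot show a borderline-to-clinical move, and no composite or total score is summarized, contrary to Protocol 10.8.7 and undeclared in SAP 3.9

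*SAP*

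**What the plan says.** Protocol 10.8.7 sets the CBCL structure: "Eight syndrome scores will be calculated from these questions, which will in turn be summarized by 2 composite scores". It then applies normative categories "for each score on the question, syndrome, and total level", and says that "categorizations based on a normative sample will be used to evaluate normal, borderline, or clinically relevant behavior". That makes two composites, a total level and three ordered categories. Protocol 12.3 adds that CBCL scores and "the respective change from primary LCM study Baseline scores will be analyzed in a descriptive manner".

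SAP 8.4.8 is narrower. In the text after Table 8–4, raw scores and change from Baseline are summarized by visit and at Last Visit for each syndrome scale of each form. No composite is defined. Overall scores are mentioned once, where T-scores are said to be determined for each subject's "raw syndrome and overall scores"; the sentence on programming the T-scores then covers syndrome scales only, and no overall score is summarized. For categories, T < 65 is Normal and T ≥ 65 is "Borderline or Clinical range (BCR"). Shift summaries "will also be provided based on the CBCL calculated T-score categories of Normal and BCR".

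SAP 3.9, on changes to protocol-defined analyses, lists two items: added subgroups, and fewer adverse event tables by 3-month interval. The CBCL is not among them.

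**The concern.** Assessing behavior is one of the study's stated other objectives, and CBCL change from Baseline is a named safety variable. The protocol says how the instrument will be reduced to composites and graded by severity. The SAP drops the composites and the total, and collapses the severity grading at the boundary between borderline and clinical.

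Two things are at stake. First, T-scores are the age- and sex-normed form of the CBCL, and the shift table is the only summary built on them. If that table cannot separate borderline from clinical, no summary table counts children who cross into the clinical range from borderline. Second, without a composite or total, each form yields eight separate syndrome summaries and no overall CBCL result.

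The omission looks unplanned. In SAP 8.4.9 the BRIEF-P and BRIEF index scores and Global Executive Composite get raw values, change and T-score shifts. Only the CBCL loses its higher-level scores, and no reason is given.

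**Working it through.** There is no planned figure to reproduce. The check sets the two documents side by side, then uses two counts.

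**Side by side**

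| Element | Protocol 10.8.7 | SAP 8.4.8 |
|---|---|---|
| Syndrome scores | Eight | Eight per form, raw value and change summarized |
| Composites | Two | None defined or summarized |
| Total level | Categorized | Mentioned in the T-score sentence, not summarized |
| Question level | Categorized | Not categorized |
| Categories | Normal, borderline, clinically relevant | Normal (T < 65), BCR (T ≥ 65) |
| Declared in SAP 3.9 | – | No |

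**Which shifts are visible.** Three ordered categories allow 3 worsening moves:

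1. Normal to borderline: appears as Normal to BCR, visible.
2. Normal to clinical: appears as Normal to BCR, visible, but indistinguishable from move 1.
3. Borderline to clinical: appears as BCR to BCR, not visible.

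So 2 of 3 worsening moves appear. The same merging hides clinical to borderline among the improving moves. Within the BCR Baseline row, the table can show only no change or a return to Normal.

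**Whether a total can be built from the syndrome scales.** Counting the entries in the SAP tables:

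- Table 8–3 (CBCL/1½-5): 19 + 8 + 5 + 9 + 7 + 11 + 8 + 33 = 100 distinct items, against 100 questions stated. The eight scales cover the form.
- Table 8–4 (CBCL/6-18): 18 + 13 + 10 + 17 + 11 + 11 + 15 + 8 = 103 distinct items, against 120 questions stated. The gap is 120 − 103 = 17.

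A CBCL/6-18 total over all questions therefore cannot be obtained by adding the eight scale scores. It has to be scored from the item-level data.

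**The case against.** The strongest reply is that the same section of the SAP already shows worsening. Raw-score change is summarized for every syndrome at each visit and Last Visit, any increase is defined as worsening whatever the Baseline category, and each subject's T-scores, raw scores and raw changes are listed. Behavior-related TEAEs are tabulated separately under SAP 8.2, and BRIEF and BRIEF-P composites are summarized. All of this stands. A reader might infer from the shift table that a child already borderline can never be shown as worsening, or that all deterioration in children starting at T ≥ 65 is invisible. The documents do not support that: the limit applies to the shift table for a given syndrome scale. Nor would a third category help a child already in the clinical range at Baseline, who has no higher category to move to.

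These outputs do not replace what is missing, however. Mean raw change pools improvers with worseners and does not count threshold crossings. Raw scores are not normed. Listings are not summaries.

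It can also be said that Protocol 12.3 promises only descriptive analysis, makes shift tables optional and leaves detail to the SAP; that one cut at 65 matches the BRIEF and BRIEF-P; and that the CBCL text was rewritten in SAP Amendment 3, which gives consistency across the pediatric program as a reason. This explains the choice of one cut. It does not explain dropping the composites and total that Protocol 10.8.7 says will be produced, and it does not remove the need to declare the departure.

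**Conclusion.** The point holds as an undeclared departure from the protocol with a limited effect. The CBCL shift tables show 2 of the 3 worsening moves between the protocol's categories, and no composite or total score is summarized for either form. The loss is confined to those tables and those missing summaries.

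The number of children affected cannot be stated. The documents give no Baseline distribution of CBCL T-scores and no cut-off separating borderline from clinical. The conclusion does not depend on that number.

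The change is worth making, but it is not critical. The CBCL is an other safety variable, not a primary one, and the study plans no hypothesis tests, so neither error rates nor sample size is involved. The proposed remedy assumes that the CBCL manual cited in SAP 8.4.8 supplies the clinical cut-point and the make-up of the composites, since neither document does.

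**What to change.** In SAP 8.4.8:

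- Replace the Normal/BCR shift categories with Normal, Borderline and Clinical, and state the cut-points from the CBCL manual.
- Define the two composites and the total score for each form, and summarize values, change from Baseline and shifts for each, with the cut-points that the manual gives for that score.
- State that the CBCL/6-18 total is scored from the item-level data, not from the eight scales of Table 8–4.
- Keep the existing restriction of change and shift summaries to assessments with a Baseline from the same questionnaire.

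In SAP 3.9, declare and justify any level in Protocol 10.8.7 that is still omitted, such as question-level categories. If the sponsor prefers to keep the single cut or to leave out the composites or total, the minimum correction is to say so there and give the reason.

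The cost is SAP wording and programming on forms already being collected. The one drawback is somewhat sparser cells in the shift tables.
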